4. PLANNED ANALYSES

The following analyses will be performed for this study:

- Final Analysis

4.1. Interim Analysis

There is no planned or unplanned interim analysis for this study.

4.2. Final Analysis

All final, planned analyses identified in this SAP will be performed following Sponsor (Arena Pharmaceuticals, Inc., hereafter referred to as Arena) authorization of the SAP, database lock, analysis sets, and unblinding of treatment. After Arena has authorized breaking of the study blind, the final analysis will be performed.

Any posthoc, exploratory analyses completed to support planned study analyses, which were not identified in this SAP, will be documented and reported in the clinical study report (CSR). Any results from these unplanned analyses will also be clearly identified in the text of the CSR ([ICH 1995](#)).

5. ANALYSIS SETS

Agreement and authorization by Arena of subjects included/excluded from each analysis set will be conducted prior to the unblinding of the study.

5.1. Screened Set

The Screened Set will consist of all subjects who sign informed consent to participate in the study.

5.2. Randomized Set

The Randomized Set will consist of all subjects who are randomized to study treatment.

5.3. Full Analysis Set

The FAS will consist of all randomized subjects who receive at least 1 dose of study treatment. Subjects will be summarized by the treatment to which they were randomized, regardless of treatment actually received.

5.4. Per Protocol Sets

The Per Protocol Set will be derived for Week 12 and Week 52, separately, and will consist of all subjects in the FAS who adhere to the protocol and complete Week 12 and Week 52, respectively. These sets will be used in sensitivity analyses of the primary and key secondary endpoints to evaluate the influences of important protocol deviations on the primary results.

Subjects may be excluded from the Week 12 Per Protocol Set if they meet any of the following criteria:

- Overall study treatment noncompliance in the first 12 weeks (< 80 or $> 120\%$)
- Receive incorrect study treatment for > 7 days in total in the first 12 weeks
- Use rescue medication (new or dose increase from the highest dose of background treatment for UC received during Screening) or undergo rescue medical procedure that may affect efficacy endpoint at Week 12

- Miss Week 12 endoscopic score (ES) in prespecified analysis window (per Section 6.4) for reasons other than UC flare, or discontinued due to disease worsening or lack of efficacy

Subjects may be excluded from the Week 52 Per Protocol Set if they meet any of the following criteria:

- Overall study treatment noncompliance (< 80 or > 120%)
- Receive incorrect study treatment for > 7 days in total
- Use rescue medication (new or dose increase from the highest dose received during Screening) or rescue medical procedure that may affect efficacy endpoint at Week 52
- Miss Week 52 ES in prespecified analysis window (per Section 6.4) for reasons other than UC flare, or discontinued due to disease worsening or lack of efficacy

Refer to [Appendix 7](#) for the definition of rescue therapies (medication and medical procedures). All protocol deviations will be reviewed in addition to the programmable deviations (eg, study treatment noncompliance) to determine if any deviation is significant enough to exclude a subject from each of the Per Protocol Sets. All exclusion flags will be finalized before study unblinding. Subjects excluded from each Per Protocol Set will be listed along with the reason category above. Subjects will be summarized by treatment to which they were randomized, regardless of treatment actually received.

5.5. Modified Full Analysis Set

The mFAS will consist of all randomized subjects who receive at least 1 dose of study treatment and have a Baseline and at least 1 postrandomization measurement. Subjects will be summarized by treatment to which they were randomized, regardless of treatment actually received. Note that the mFAS can vary between endpoints since some subjects may have the data needed for inclusion in the mFAS for some endpoints, but not other endpoints. Also note, since the Mayo component scores on the disease worsening CRF are manually entered by sites from another CRF, these scores will not be used in the derivation of mFAS for measurement of either MMS or any of its component scores.

5.6. Safety Set

The Safety Set will include all randomized subjects who receive at least 1 dose of study treatment. Subjects will be analyzed according to treatment received, regardless of randomization. The Safety Set will be used for all safety analyses.

5.7. Pharmacokinetic Set

The Pharmacokinetic Set will include all subjects in the Safety Set with at least 1 quantifiable postdose etrasimod concentration which is not impacted by protocol violations or events with potential to affect the etrasimod concentration.

6. GENERAL CONSIDERATIONS

6.1. Reference Start Date and Study Day

Study Day will be calculated from the reference start date and will be used to show start/stop day of assessments and events. Reference start date is defined as the date of first dose (Day 1) and will appear in every listing where an assessment date or event date appears.

- If the date of the event is on or after the reference start date, then:

$$\text{Study Day} = (\text{date of event} - \text{reference start date}) + 1$$

- If the date of the event is prior to the reference start date, then:

$$\text{Study Day} = (\text{date of event} - \text{reference start date})$$

In the situation where the event date is partial or missing, Study Day and any corresponding durations will appear missing in the listings.

6.2. Baseline

Unless otherwise specified, Baseline is defined as the last nonmissing measurement taken prior to the first dose (including unscheduled assessments). If measurements include time (except for health-related quality of life [HRQoL] instruments), the date/time will be used to define Baseline. Otherwise, only dates will be compared. For HRQoL instruments, only the date will be used to derive Baseline. In the case where the last nonmissing measurement and the date of first dose coincide and time is not collected, if the measurement was planned in the protocol to be done prior to the date of first dose, that measurement will be considered in defining Baseline.

6.3. Retests, Unscheduled Visits, and Early Termination Data

For by-visit analyses and summaries, efficacy, safety, HRQoL, and biomarker data (including scheduled, retests, unscheduled, and early termination) will be assigned to visits after the application of the windowing conventions described in Section 6.4. All measurements will be considered in summaries of abnormalities or worst-case values post-Baseline.

The visit windowing will be applied before missing data are imputed.

Listings will include scheduled, unscheduled, retest, and early termination data.

6.4. Windowing Conventions

All scheduled study visits are defined relative to Study Day 1, the date of first dose. Scheduled visit windows are defined in Clinical Study Protocol APD334-301 Appendix 1. A windowing convention will be used to determine the analysis visit value for a given measurement and will be applicable for all by-visit summaries and analyses for efficacy and safety data. Refer to [Table 2](#) for specific visit windows.

Table 2: Visit Windows for Efficacy and Safety Analyses

For all efficacy (except endoscopy/MMS/histology), efficacy-related biomarkers, safety labs and vital signs	
Scheduled Study Visit (Protocol Scheduled Day)	Analysis Visit Window (Study Day)
Baseline	≤ 1
Week 0 (Day 1)	1
Week 0 (Day 2) ^a	2
Week 2 (Day 15 ± 3)	2 to 22, or 3 to 22 ^a
Week 4 (Day 29 ± 3)	23 to 43
Week 8 (Day 57 ± 3)	44 to 71
Week 12 (Day 85 ± 7)	72 to 99
Week 16 (Day 113 ± 7)	100 to 127
Week 20 (Day 141 ± 7)	128 to 155
Week 24 (Day 169 ± 7)	156 to 197
Week 32 (Day 225 ± 7)	198 to 253
Week 40 (Day 281 ± 7)	254 to 309
Week 48 (Day 337 ± 7)	310 to 351
Week 52 (Day 365 ± 14)	> 351
For endoscopy/MMS/histology/all composite endpoints that include an endoscopy component and/or RB/SF component, Physician’s Global Assessment, health-related quality of life, ECGs, OCT, and PFT	
Scheduled Study Visit (Protocol Scheduled Day)	Analysis Visit Window (Study Day)
Baseline	≤ 1
Week 0 (Day 1)	1
Week 0 (Day 2) ^a	2
Week 12 (Day 85 ± 7) ^{b,c}	66 to 113 (66 to 141 for assessments impacted by COVID-19 pandemic) ^d
Week 32 (Day 225 ± 7) [PFT only]	198 to 253 (198 to 281 for assessments impacted by COVID-19 pandemic) ^d
Week 52 (Day 365 ± 14) ^{b,d}	337 to 393 (337 to 421 for assessments impacted by COVID-19 pandemic) ^e

^a Applicable only for subjects who require extended monitoring on Day 2 for vital signs and ECGs.

^b Applicable to all Week 12 and Week 52 efficacy endpoints based on any component of Mayo clinic score, such as clinical remission and symptomatic remission. Protocol visit window for PFT and OCT at Week 12 is Day 85 ± 7 (FDA 2020).

^c Due to overlapping windows at Week 12 and Week 8/16, a hierarchical algorithm will be used for the mapping. Week 12 will always be mapped first, then assess records for the Week 8/16 mapping. If a scheduled Week 8 and 12, or Week 12 and 16 visits are both present in the same visit window, they will be mapped to separate visits (ie, Week 8 and Week 12 or Week 12 and Week 16).

^d Due to overlapping windows in the RB/SF components at Week 52 and Week 48, a hierarchical algorithm will be used for the mapping. Week 52 will always be mapped first, then assess records for the Week 48 mapping. If a scheduled Week 48 and 52 visits are both present in the same visit window, they will be mapped to separate visits (ie, Week 48 and Week 52).

^e Assessments impacted by the COVID 19 pandemic are reported in the Date of Visit eCRF.

COVID-19, coronavirus disease 2019; ECG, electrocardiogram; eCRF, electronic case report form; MMS, modified Mayo Score; OCT, optical coherence tomography; PFT, pulmonary function test; RB, rectal bleeding; SF, stool frequency.

For cardiac remonitoring upon treatment reinitiation after Day 2, as manifested by more than 1 timed measurement in vital signs or electrocardiogram (ECG) parameters on the same collection date of an unscheduled visit, measurements will be mapped to analysis visit of Cardiac Remonitoring 1, Cardiac Remonitoring 2, etc. in the respective analysis dataset. For analysis, each timed measurement will be programmatically assigned to the nearest hourly timepoint (eg, Predose, 1-hour Postdose) based on their relationship to the dosing time on the same day. If the dosing date/time on the same day is missing, the timepoint will remain missing. Once mapped, these timed measurements from cardiac remonitoring visits will not be considered for any other analysis visit.

Windowing will be applied prior to any missing data calculations. The last nonmissing measurement taken prior to Day 1 (including unscheduled assessments) will be labeled as “Baseline”. Unless stated otherwise, data from all visits including scheduled, unscheduled, and ET visits will be eligible for allocation to an analysis visit. The 2-Week and 4-Week Follow-Up visits will not be included in the visit windows and will be summarized separately without any window applied.

If one or more results for a variable are assigned to the same analysis visit, the result with the date closest to the protocol scheduled day will be used in the analysis, except for component subscores of MMS or TMS, in which case, the composite score and component subscores from the same date will be used in the analysis. If 2 measurements in the same analysis visit window are equidistant from the protocol scheduled study day, the earliest measurement will be used in the analysis. If multiple assessments are available on the same day, then the average of the assessment will be used in the analysis, except for laboratory and ECG data where the assessment at the earliest time of the same day will be used. If both central and local assessments of the same ECG or lab test are available on the same day, the central result will take precedence over the local result.

For the overlapping visit windows at Week 12 and Week 8/16, a hierarchical algorithm will be applied as follows: always map to the Week 12 study visit if the study day falls within the visit window of the Week 12 study visit, then assess the other records for the Week 8 or Week 16 study visit. The same algorithm will be used for Week 48 and Week 52, with Week 52 taking priority.

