1.3. Benefit/Risk Assessment

Considering the significant unmet need for safe and effective, orally administered treatments for UC, etrasimod may potentially provide therapeutic benefit via S1P receptor modulation.

Adverse events that have been reported with S1P receptor modulators include bradycardia at the first dose or atrioventricular (AV) block, macular edema, hypertension, headache, cough, dyspnea, back pain, influenza, and diarrhea.

Safety and tolerability of etrasimod has been evaluated in Phase 1 studies with healthy adult subjects at single doses up to 5 mg and repeated doses up to 4 mg once daily. Repeated doses of 2 mg have been evaluated in Phase 2 studies of subjects with moderately to severely active UC (refer to the current edition of the IB). Etrasimod was found to be safe and well tolerated in these studies, with no clinically significant safety concerns with respect to vital signs, electrocardiograms (ECGs), pulmonary function tests (PFTs), ophthalmoscopy, or clinical laboratory tests. Etrasimod produced a dose-dependent sustained decrease in total lymphocyte count, which is expected given etrasimod's mechanism of action. Lymphocyte counts were within normal limits by 7 days after the last dose.

Detailed information regarding the known and expected benefits and risks and reasonably expected adverse events of etrasimod can be found in the IB.

Based on the mechanism of action of etrasimod and prior experience with other agents acting via a similar mechanism, monitoring for specific safety parameters are planned for this study, which include: auscultation of the lungs as part of the physical exam; PFT, exclusion of subjects with macular edema or retinopathy, with assessment of optical coherence tomography (OCT) occurring throughout the study; and exclusion of subjects with certain cardiac risks, with assessment of vital signs in the period following dosing.

- Auscultation of lungs will be conducted as part of the physical examination.
- Prospective subjects with a history of macular edema or retinopathy will be excluded from the study. All randomized subjects will be assessed by OCT at study entry, periodically throughout the treatment period, and as clinically indicated any time during the study.

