Subjects who discontinue treatment prematurely, regardless of the reason, should be instructed to return for an Early Termination (ET) visit within 7 days of the last administration of study treatment (Table 7 and Table 8) and before initiation of any new treatments to complete all of the ET assessments. If a subject discontinues due to pregnancy, they are not required to complete the endoscopy. If the ET visit is within 4 weeks of the last sigmoidoscopy and biopsy, these procedures do not need to be repeated.

If the ET visit is ≥ 2 weeks of the last administration of study treatment, the 2-Week Follow-Up visit is not required; however, the 4-Week Follow-Up visit should be scheduled and completed. If the ET visit is ≥ 4 weeks of the last administration of study treatment, the 4-Week Follow-Up visit is not required unless the absolute lymphocyte count (ALC) is not within normal limits.

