9.5. Follow-Up Period

For subjects not participating in the OLE study, a follow-up visit, will be performed at 2 and 4 weeks after the last administration of study treatment as indicated in the Schedules of Assessments (Table 7 and Table 8).

If the ET or Study Completion visit is ≥ 2 weeks after the last administration of study treatment, the 2-Week Follow-Up visit is not required; however, the 4-Week Follow-Up visit should be

scheduled and completed. If the ET or Study Completion visit is ≥ 4 weeks after the last administration of study treatment, the 4-Week Follow-Up visit is not required.

If the absolute peripheral lymphocyte count is not within normal limits at the 4-Week Follow-Up visit, subjects should return for CBC with differential according to local standard of care (captured as subsequent Follow-Up visit or unscheduled visit).

All adverse events should be recorded for 30 days after last administration of study treatment (Section 9.10.8.2.2).

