18.3.1. Safety Laboratory Evaluations

Hematology, serum chemistry, coagulation, and urinalysis are analyzed and reported by central laboratory and sometimes by local laboratory. Results out of reference range are flagged by the performing laboratory (eg, low, high). A full list of laboratory assessments to be included in the outputs is included in Clinical Study Protocol APD334-301 Table 6.

In general, presentations will use SI units. Quantitative laboratory measurements reported as “< X” or “> X”, where X may be the lower limit of quantitation (LLQ) or the upper limit of quantitation (ULQ), respectively, will be converted to X for the purpose of quantitative summaries, but will be presented as recorded, ie, as “< X” or “> X” in the listings. For urinalysis, only pH and specific gravity are considered as quantitative tests. If local and central laboratory assessments are available from the same day, central laboratory assessments will be used in the summary as per Section [6.4](#).

The following summaries will be provided for laboratory data:

- Value and change from Baseline by visit (for hematology, serum chemistry, quantitative urinalysis [pH and specific gravity], and coagulation)

- Incidence of abnormal values according to laboratory reference ranges by visit
- Incidence of lymphocytes $< 0.2 \times 10^9/L$, $0.5 \times 10^9/L$, or neutrophils $< 0.5 \times 10^9/L$, $1 \times 10^9/L$ at end of treatment and anytime in the study
- Shift from end of treatment to each follow-up visit in incidence of lymphocytes in normal range and in incidence of lymphocytes of at least 80% percent of Baseline, by visit (2-Week Follow-Up, 4-Week Follow Up, and Last Follow-Up)
- Shift from Baseline to end of treatment according to laboratory reference range (for quantitative measurements and categorical measurements)
- Evaluation of drug-induced serious hepatotoxicity (eDISH) plots for the following laboratory assessments (using values after the first administration of study treatment):
 - Maximum aspartate aminotransferase (AST) versus same-day total bilirubin
 - Maximum alanine aminotransferase (ALT) versus same-day total bilirubin
 - Maximum gamma-glutamyl transferase (GGT) versus same-day total bilirubin
 - Maximum alkaline phosphatase (ALP) versus same-day total bilirubin

The eDISH plots above will be repeated with adjustment for elevated Baseline.

- Incidence of hepatic enzyme elevations by visit

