All subjects are expected to achieve steady-state plasma concentration by Week 2. For each subject, the average steady-state trough (predose) plasma concentration based on Week 2 to Week 52 trough concentrations ($C_{\text{trough,ss,W2-W52}}$) per subject will also be calculated and presented in a data listing and summarized using descriptive statistics.

Mean (\pm SD) etrasimod concentration versus nominal time (Weeks 0 to 52) will be plotted on linear scales. Additionally, a mean (\pm SD) concentration-time plot with etrasimod and metabolites overlaid on linear and semi-logarithmic scale will be generated.

Box plots of etrasimod, M3, and M6 concentrations at Day 1, 4-hour postdose timepoint (C_{4h}), steady-state C_{trough} (Weeks 2 through 52), and $C_{\text{trough,ss,W2-W52}}$ will be plotted versus nominal timepoint on ordinal scale.

Individual subject plasma concentrations versus actual time (Weeks 0 to 52) will be plotted since start of treatment on linear and semi-logarithmic scales. Individual subject plots with etrasimod and metabolite concentration data will be overlaid on the same plot.

Scatter plots of individual subject average steady-state $C_{\text{trough,ss,W2-W52}}$ versus Baseline body weight and versus Baseline age (age at consent) as continuous variables will be generated for the Pharmacokinetic Set, which will also include the Spearman's rank correlation coefficient, p-value, and locally estimated scatterplot smoothing (LOESS) trend line.

To explore potential etrasimod plasma exposure-response relationships, the following scatter plots will be generated for the Safety Set, including data from placebo subjects (plotted at 'zero' concentration). Any contributing data from the placebo subjects will be annotated with a different color or symbol. All scatter plots will include the Spearman's rank correlation coefficient, p-value, and LOESS trend line (based on subjects that received active treatment only).

- Individual subject absolute change from Baseline in MMS versus etrasimod steady-state C_{trough} at Week 12
- Individual subject absolute change from Baseline in MMS versus etrasimod steady-state C_{trough} at Week 52
- Individual subject lymphocytes versus etrasimod steady-state C_{trough} at Week 52 and grouped all visits (Weeks 2 through 52 pooled)

- Individual subject absolute changes from Baseline in lymphocytes versus etrasimod steady-state C_{trough} at Week 52 and grouped all visits (Weeks 2 through 52 pooled)

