APPENDIX 1: PROGRAMMING CONVENTIONS FOR OUTPUTS

OUTPUT CONVENTIONS

Outputs will be presented as shown in the Output shells.

DECIMALS, PERCENTAGES, AND P-VALUES

- If the original data has N decimal places, then the summary statistics should have the following decimal places:
 - Minimum and maximum: N
 - Mean (and LS Means), median: N + 1
 - SD or SE: N + 2
- Percentages will be reported to one decimal place. Where counts are zero, percentages will not appear in the output.
- P-values will be reported to three decimal places, except values < 1.000 but > 0.999 will be presented as ' > 0.999 ' (eg, 0.9998 is presented as > 0.999).
- Values < 0.001 will be presented as ' < 0.001 ' (eg, 0.0009 is presented as < 0.001). Rounding will be applied after the < 0.001 and > 0.999 rule.

CONVENTIONS RELATED TO PHARMACOKINETIC DATA

All etrasimod concentrations will be reported and analyzed with the same precision as the source data provided by the bioanalytical laboratory regardless of how many significant figures or decimals the data carry. The derived PK data (etrasimod concentration) will be rounded to carry 3 significant digits and considered the source data for the calculation of descriptive statistics and the statistical analysis source data.

For the reporting of descriptive statistics, the mean, geometric mean, median, SD, % CV, and % geometric CV will be presented with 4 significant digits. The minimum and maximum will be presented with 3 significant digits.

DATES AND TIMES

Depending on data available, dates and times will take the form DDMMYYYY or DDMMYYYY:hh:mm.

SPELLING FORMAT

English US.

PRESENTATION OF TREATMENT GROUPS

For outputs, treatment groups will be represented as follows and in that order:

Treatment Group	For Tables, Graphs, and Listings
Etrasimod	Etrasimod
Placebo	Placebo
Screen Failure	Screen Failure
Not Treated ^a	Not Treated

^a To be used for subjects in safety listings who are randomized but do not receive study treatment.

PRESENTATION OF VISITS AND STUDY PERIOD

For outputs, visits and study periods will be represented as follows and in that order:

Visit Name	Study Period
Screening	Screening
Baseline, Day 1, Week 2, Week 4, Week 8, Week 12, Week 16, Week 20, Week 24, Week 32, Week 40, Week 48, and Week 52	Treatment
End of Study/Early Termination	Dependent on Analysis Visit assigned, described in Section 6.4
2-Week Follow-Up, 4-Week Follow-Up	Follow-Up

LISTINGS

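### SAP 6.4 has no last-dose condition, so off-drug lymphocyte counts can be analysed as on-treatment visit values, and SAP 20 does not say whether Early Termination PK samples are steady-state troughs

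*SAP*

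**What the plan says.** SAP 6.3 and 6.4 assign efficacy, safety and biomarker results, including retests, to analysis visits by study day: "data from all visits including scheduled, unscheduled, and ET visits will be eligible for allocation to an analysis visit". Within a window, the result nearest the scheduled day is used. In Table 2 the Week 52 window for laboratory and biomarker data is open-ended (after Day 351). The only off-drug data kept out are defined by label: "The 2-Week and 4-Week Follow-Up visits will not be included in the visit windows and will be summarized separately without any window applied". Appendix 1 gives the study period of an ET visit as "Dependent on Analysis Visit assigned, described in Section 6.4", so a windowed ET visit becomes a treatment-period visit.

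Protocol 5.1 says that subjects who stop early "should be instructed to return for an Early Termination (ET) visit within 7 days of the last administration of study treatment". Later ET visits are foreseen. Protocol 9.5 waives the 2-Week Follow-Up when ET comes 2 weeks or more after the last dose, and has a further rule beginning "If the ET or Study Completion visit is ≥ 4 weeks after the last administration of study treatment". Protocol Tables 7 and 8 schedule a blood count and a PK sample in the ET columns. On recovery, Protocol 1.3 says: "Lymphocyte counts were within normal limits by 7 days after the last dose".

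SAP 19 models lymphocyte change by visit. SAP 18.3.1 tabulates "Shift from end of treatment to each follow-up visit in incidence of lymphocytes in normal range". SAP 20 calculates for each subject "the average steady-state trough (predose) plasma concentration based on Week 2 to Week 52 trough concentrations" and plots lymphocytes against trough, pooled over Weeks 2 to 52, with a Spearman coefficient and p-value.

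**The concern.** A count taken after lymphocytes have returned to normal is not an on-treatment count, yet the windowing rule treats it as one. The same blood sample is excluded if the visit is labelled 2-Week Follow-Up and counted as Week X if it is labelled ET. When ET is late, it replaces the follow-up visit that would have been excluded.

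At stake is the description of the drug's main pharmacodynamic effect. The by-visit lymphocyte change would be pulled toward zero. The shift from end of treatment to follow-up could start from a count that has already recovered, and so miss the recovery it is meant to show. If ET concentrations are taken as troughs, low concentrations pair with recovered counts in the exposure-response plots for a reason unrelated to exposure at steady state.

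**Working it through.** **1. The rule.** SAP 6.3, 6.4, 18.3, 19 and 20 contain no last-dose or time-since-dose limit for laboratory or biomarker values. SAP Appendix 7 does start the follow-up period at the last dose, but only for classifying rescue therapy. An example: a subject stopped on Day 1 after cardiac monitoring (Protocol 5.1) has ET on Day 8. Table 2 maps Days 2 to 22 to Week 2, so a count taken after one dose and 7 days off drug becomes that subject's Week 2 value.

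**2. End of treatment.** SAP 18.3.1 does not define the term. The protocol's abbreviation list expands ET as 'End-of-treatment', while the body text uses ET for Early Termination. Using the ET value is therefore a natural reading, though not a stated one.

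**3. Size of the lymphocyte bias.** The plan gives no figure on this point. Inputs from the plan are 280 etrasimod subjects (SAP 7) and a projected overall dropout of 50% (SAP 16.1.4.1). The latter was used to choose 40 imputations: 1/(1 + 0.5/40) = 0.988, which matches the stated relative efficiency of about 99%. Because it was not a forecast of ET visits, dropout d is varied from 20% to 50%.

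Assumptions: leavers are spread evenly over the 11 post-baseline windows; each gives one ET sample, which is the value used in its window; a share s of ET samples (25% to 100%) is off drug; those counts have recovered by r (50% to 100%).

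- Leavers per window: m = 280d/11
- Off-drug share, last window: f = m·s / (280(1 − d) + m)
- Off-drug share, all windows pooled: 280·d·s / (11·280 − 66m + 280d)
- Observed mean change = (1 − f)Δ + f(1 − r)Δ = Δ(1 − f·r)

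For d = 50% and s = 100%: m = 12.73; f = 12.73/(140 + 12.73) = 8.3%; pooled share = 140/(3080 − 840 + 140) = 5.9%.

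| d | s | pooled share | last-window f | shrinkage, r = 50% | shrinkage, r = 100% |
|---|---|---|---|---|---|
| 20% | 25% | 0.5% | 0.6% | 0.3% | 0.6% |
| 20% | 100% | 2.0% | 2.2% | 1.1% | 2.2% |
| 50% | 25% | 1.5% | 2.1% | 1.0% | 2.1% |
| 50% | 100% | 5.9% | 8.3% | 4.2% | 8.3% |

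If the true mean fall were 50% (an assumed value), the last-window estimate would lie between 50 × (1 − 0.083) = 45.8% and 50 × (1 − 0.003) = 49.9%.

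**4. Exposure-response, if ET samples are entered as troughs.** Simulation of 280 subjects, 150 replicates per setting, with no true on-drug relation. Further assumptions: half-life 24 or 48 h (the documents give none), trough CV 40%, lymphocytes halved on drug, recovery linear on the log scale by day 7, off-drug ET samples 1 to 7 days after the last dose.

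| d | s | mean pooled Spearman rho |
|---|---|---|
| 20% | 25% | about -0.01 |
| 20% | 100% | -0.03 to -0.04 |
| 50% | 25% | about -0.02 |
| 50% | 100% | about -0.09 |

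With the off-drug pairs removed, mean rho is -0.007 to 0.004, with a replicate SD of about 0.05. With the 2,380 pooled pairs of step 3 treated as independent, nominal p < 0.05 needs |rho| of only about 1.96/√2380 = 0.04. The replicate SD shows that repeated measures alone would often exceed that, so the p-value is fragile for a second reason.

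**The case against.** Most of the case against is fair, and it narrows the point.

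- **PK.** A reader might infer that the SAP counts ET samples as steady-state troughs. It does not say so. The windowing text and Table 2 never name concentrations. SAP 20 summarises by nominal timepoint, lists time since last dose, and lets the pharmacokineticist exclude affected data case by case. Protocol 9.7 defines a trough as a sample within 60 minutes before dosing, which a subject who has stopped cannot supply. Against that, Tables 7 and 8 put the sample in shared Week 12/ET and Week 52/ET columns, the exclusion is optional, and an ET visit within 7 days is no deviation. The SAP leaves a gap; it gives no instruction.
- **Exposure-response.** The plots are exploratory, and Protocol 1.3 reports a dose-dependent lymphocyte decrease, so a correlation need not be false. What stands is that off-drug pairs add correlation that does not come from variation in steady-state exposure.
- **Unscheduled samples.** SAP 18.3 leaves local laboratory counts out of summaries, and blood counts after the 4-Week Follow-Up follow local standard of care in subjects not yet normal. Only centrally tested off-drug samples matter.
- **Not every ET value counts.** A nearer on-drug value in the same window takes precedence, some leavers are kept on blinded drug until the extension study (Table 8 footnote), and subjects who are lost may give no sample. The upper figures above are therefore ceilings.
- **Estimand.** No aim is stated for biomarkers, and a treatment-policy aim would keep off-drug values. But it would then also keep an early leaver's 2-Week Follow-Up count, which the SAP excludes. Selection by visit label fits neither aim.

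**Conclusion.** The point holds for lymphocytes. As written, the SAP allows off-drug ET counts, and off-drug unscheduled counts tested centrally, to be analysed as Week 2 to Week 52 values. The bias is toward no effect and modest: 0.3% to 8.3% of the mean change in the last window, for dropout of 20% to 50%, 25% to 100% of ET samples off drug and 50% to 100% recovery. The effect on the end-of-treatment shift is conditional on ET being taken as end of treatment. The effects on the trough average and on the exposure-response plots (rho about -0.01 to -0.09) are conditional on ET samples being admitted as troughs and on the assumed half-lives.

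Two wider readings are not supported. Dilution of hs-CRP or fecal calprotectin is not shown: the documents give an off-drug recovery time only for lymphocytes, and whether to include off-drug values of those markers is a choice of estimand. The primary and key secondary endpoints are not touched, and no biomarker or PK result enters the alpha-controlled testing. This is an inexpensive improvement to the pharmacodynamic and PK reporting; the trial's main conclusions do not depend on it.

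**What to change.** - **SAP 6.4, 18.3.1 and 19:** allocate a lymphocyte value to an on-treatment visit only if it was taken within a prespecified short time after the last dose and not during a dose interruption. Report later values in a separate off-treatment summary.
- **SAP 18.3.1:** define end of treatment as the last value that meets this rule.
- **SAP 20:** admit a sample to the steady-state trough average and to the exposure-response plots only if its time since last dose fits a once-daily trough and dosing had been uninterrupted long enough for steady state. State how ET samples are handled.
- Keep the all-values version as a sensitivity summary.

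The cost is wording and programming. The last-dose date and interruptions (SAP 14) and the time of the last dose before each PK sample (Protocol 6.3 and 9.7) are already recorded. The downside is slightly fewer values per visit.
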